9.4 Analysis visit windows

Each participant will be followed up till Day 43 (\pm 2 days) or the day of premature discontinuation, including 4 continuous days (72 hours post first dose) in the hospital after admission, followed by 5 out-patient visits on Days 8, 15, 22, 29, and 43 (or day of premature discontinuation).

The time window is \pm 30 minutes for each scheduled timepoint on Day 1 through Day 4. The visit window is \pm 1 day for Day 8 and \pm 2 days for Days 15, 22, 29 and 43.

In case any assessment occurs outside of the defined timepoint/visit window, it will be allocated to “unscheduled”. These visits will not be included in descriptive statistics by nominal visit or time point and will be flagged in subject data listings. In case too many measurements are observed outside of the defined visit windows, it will be decided on an individual basis whether those can be allocated to scheduled visits in a reasonable manner during data review before database lock.

9.5 Software

All the analyses will be performed in SAS[®] software version 9.4 or higher.

9.6 Data Handling After Cut-off Date

By its nature, data after cut-off may be incomplete and subject to further change and will not be used for summary statistics, statistical analyses, listings or imputations.

Stop dates are not affected by this rule, e.g. a stop date of AEs, which starts prior to the cut-off, but stops after date of cut-off, will not be changed.

9.7 Definition of Baseline and Change from Baseline

In general, the last non-missing scheduled measurement prior to the first study intervention administration will be used as the baseline measurement.

If an assessment is planned to be performed before study intervention per protocol but the assessment time is not available, it will be assumed that it was performed prior and considered as baseline.

If a scheduled pre-dose measurement actually occurred post-dose, then the corresponding measurement will be analyzed similarly to an unscheduled post-dose measurement.

Absolute and percent changes from baseline are defined as

$$\text{absolute change} = \text{visit value} - \text{baseline value}$$

$$\text{percent change} = 100 * (\text{visit value} - \text{baseline value}) / \text{baseline value}$$

9.8 Study Day / Study Intervention Day

If endpoints refer to specific timepoints, the timepoints given refer to days after treatment. Thereby, time of treatment start is defined to be on Day 1. Study day is defined relative to Day 1. If an endpoint defines the measurement to be taken, e.g., 7 days after treatment, this means that the measurement is taken on Day 8.

9.9 Definition of Duration, 'Time to' and 'Time Since' Variables

Duration will be calculated as the difference between start and end dates plus 1 (e.g., the duration of an Adverse Event (AE) = AE end date – AE start date + 1). Durations will be calculated only when both dates are available, i.e. imputed dates will not be used to compute the duration unless otherwise specified.

The time to an event will be calculated as date of event – reference date + 1 (e.g., ADT – STARTDT + 1). If time to an event is calculated in hours, then it is calculated as the difference between event and reference SAS datetimes divided by 3600 (e.g., (ADTM – STARTDTM) / 3600).

The time since an event will be calculated as:

- Date of event – reference date + 1, if the date of event is equal or greater than the reference data (e.g., days in study at onset of AE = AE start date – date of randomization + 1)
- Reference date – date of event otherwise (e.g., days since diagnosis = date of randomization – date of diagnosis)

9.10 Conversion Factors

The following conversion factors will be used to convert days into months or years:

$$1 \text{ week} = 7 \text{ days}, 1 \text{ month} = 30.4375 \text{ days}, 1 \text{ year} = 365.25 \text{ days}.$$

9.11 Date of Last Contact

The date of last contact will be derived for participants not known to have died at the analysis cutoff or database lock using the latest complete date prior to or at the data cutoff or database lock date among the following:

- Date of last AE start date
- Date of last blood sample
- Date of last ECG or vital sign assessment
- Date of last temperature or malaria signs and symptoms assessment

Only dates associated with actual examinations of the participant reported in the eCRF will be used in the derivation. Dates associated with a technical operation unrelated to participant status such as the date a blood sample was processed will not be used.

9.12 Definition of On-treatment Period

The on-treatment period is defined as the time from the date of first dose of study intervention to the date of premature study termination, end of study visit date or database lock date or death, whichever occurs first.

9.13 Imputation of Missing Data

No action will be taken to handle missing data. A participant who withdraws prior to the last planned observation in a study period will be included in the analyses up to the time of discontinuation.

Unless otherwise specified, all data will be evaluated as observed, and no imputation method for missing values will be used.

To determine treatment-emergent AEs, incomplete AE-related start dates will be imputed as follows:

- In case the onset date is missing completely or missing partially but the onset month and year, or the onset year, are equal to the start of study intervention then the onset date will be imputed by the minimum of start of study intervention and AE resolution date (if not missing). If AE resolution date is completely or partially missing, then the study intervention date will be used.
- In all other cases, the missing onset day or missing onset month will be imputed by 1.

Incomplete or missing AE stop dates will not be imputed, since no durations of AEs are planned to be derived.

Missing or partially missing dates for Medical History will not be imputed.

In order to allocate medications to either previous or concomitant, the following imputation rules for (partially) missing start dates will be applied:

- If the day is missing, it will be imputed by the 1st day of the month.
- If both day and month are missing the date will be imputed by 1st January.
- If the date is completely missing, no imputation will be performed.

10 Study Participants

The subsections in this section include specifications for reporting participant disposition and study intervention/study discontinuations. Additionally, procedures for reporting protocol deviations are provided.

10.1 Disposition of Participants and Discontinuations

The following will be presented in a summary table:

- Total number of participants screened (i.e., participants who gave informed consent)
- Number of screened participants who discontinued from the trial prior to enrollment
 - Participant did not meet all eligibility criteria
 - Withdrew consent
 - Progressive disease
 - Lost to follow-up
 - Death
 - Other
- Number of enrolled participants
- Number of enrolled participants who did not receive treatment (as applicable)
- Number of treated participants
- Number and percentage of treated participants who completed study
- Number and percentage of treated participants who discontinued the study, with the primary reason of discontinuation by treatment and overall

A frequency table displaying the number of participants of the different Analysis Sets will be provided.

10.2 Protocol Deviations

10.2.1 Important Protocol Deviations

Important protocol deviations will be identified for all participants by either site monitoring, medical review processes or programming and confirmed prior to or at the Data Review Meeting at the latest.

Any important protocol deviation is documented in SDTM datasets whether identified through site monitoring, medical review or programming. The management of protocol deviations is outside of this IAP document.

A frequency table as well as a listing of important protocol deviations, will be provided based on the FAS.

10.2.2 Reasons Leading to the Exclusion from an Analysis Set

A frequency table organized according to reason for exclusion from the PK analysis set, as well as a listing, will be provided.

11 Demographics and Other Baseline Characteristics

11.1 Demographics

A summary table of demographic characteristics will be provided including age, sex, race, and ethnicity.

11.2 Medical History

The medical history will be summarized from the “Medical History” eCRF page, using the most recent MedDRA version at time of database lock, preferred term as event category and system organ class (SOC) body term as Body System category. Each participant will be counted only once within each PT or SOC.

Medical history will be displayed in terms of frequency tables: ordered by primary SOC and PT in alphabetical order. A listing displaying Medical History by participant will be provided.

11.3 Other Baseline Characteristics

Summary and frequency tables, as applicable, will be provided for baseline ECG results (number of participants with abnormal ECG findings and summary statistics of ECG results for participants with abnormal findings), height, weight, BMI, vital signs, and laboratory results.

12 Previous or Concomitant Therapies

Previous medications are defined as any medication discontinued prior to the administration of study intervention. If the date values do not allow a medication to be classified as previous

medication (e.g. due to missing dates which are not imputed; see Section 9.13), the medication will be considered as a concomitant medication.

Concomitant medications are defined as any medication taken during the course of the study, with a starting date greater than or equal to the administration of study intervention, or with a starting date prior to the administration of study intervention and ongoing at the time of the administration of study intervention.

The World Health Organization Drug dictionary (WHO-DD) current version at the date of data cut-off will be used for coding of prior and concomitant medications and they will be described using Preferred Term (PT) as applicable.

A frequency table of previous and concomitant medications will be provided by ATC level 2 and PTs sorted by ATC and PTs in alphabetical order.

Previous and concomitant medications will be listed. Concomitant procedures, if any, will also be listed.

13 Study Intervention: Compliance and Exposure

M5717 + pyronaridine will be administered once as single dose on Day 1, when the participants are hospitalized. Thus, compliance for the combination is not applicable.

A frequency table displaying intake of study treatment, reasons for not taking study treatment and number of participants with different dose combinations of M5717 and pyronaridine will be provided.

14 Efficacy Analyses

14.1 Crude and PCR-adjusted ACPR at Various Timepoints

Crude ACPR 28 and 42 days after first dose is defined as absence of parasitemia (parasite count = 0) from thick smear/microscopy, irrespective of axillary temperature, in participants who did not previously meet any of the criteria of ETF, LCF, or LPF.

PCR-adjusted ACPR 28 and 42 days after first dose is defined as absence of parasitemia (parasite count = 0) from thick smear/microscopy after adjustment for parasitemia due to new infections as determined by genotyping using PCR techniques, irrespective of axillary temperature, in participants who did not previously meet any of the criteria of ETF, LCF, or LPF. By PCR-adjustment all participants with parasitemia due to a new infection are considered responders. Note that PCR-adjusted ACPR 28 days after first dose is the endpoint of the primary estimand for Part B Cohort B0.

In order to derive the population-level summary of the estimands, different intercurrent events (ICEs) will be considered. ICE as defined by the study protocol will be identified and handled as described in the following if the ICE takes place before 28 or 42 days post treatment:

- **Intake of rescue medication:** Filtering concomitant medications programmatically for all artemisinin-based combination therapies (artemether-lumefantrine, artesunate-amodiaquine, dihydroartemisinin-piperaquine, artesunate-sulphadoxine-pyremethamine), chloroquine, quinine, halofantrine, primaquine and by medical review. A composite variable strategy is applied, i.e., the primary endpoint is considered as failure (= presence of parasitemia and no ACPR).
- **Intake of prohibited medication that impacts treatment effect (e.g., drug with antimalarial activity) at any timepoint:** A treatment policy strategy is applied, i.e., treatment effect is estimated regardless of the ICE.
- **Experience of any event that affects absorption (i.e., vomiting within the study intervention absorptive period of $2 \times \text{median tmax}$) or immune response (severe immunocompromised participants):** Filter AE data programmatically for preferred term (PT) “Vomiting” within the System Organ Class (SOC) “Gastrointestinal disorders” and by medical review. A treatment policy strategy is applied, i.e., treatment effect is estimated regardless of ICE.
- **Premature study discontinuation due to lack of efficacy:** Participants who have primary reason for early termination set as “Lack of efficacy” on Study Termination eCRF. A composite variable strategy is applied, i.e., endpoint is considered as failure.
- **Death due to malaria:** Filter SAEs programmatically for fatal events with outcome “death” and by medical/safety review. Death cases for which the primary reason is ticked as “progressive disease and/or disease-related condition” qualify as death due to malaria. A composite variable strategy is applied, i.e., endpoint is considered as failure.

Participants who did not previously meet any criteria of ETF, LCF, or LPF, have no ICE, and are missing parasitemia data at the specified timepoint after first dose will be included in the denominator of the proportion and will be counted as ‘N/A’ in the summary table.

The population-level summaries are the proportion of participants achieving PCR-adjusted/Crude ACPR 28/48 days after first treatment (ACPR rates). ACPR rates will be estimated with 95% confidence intervals. Confidence intervals will be derived by use of Wilson’s score method.

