Visit Number	SCR	Visit 1	Visit 2	Visit 3	Visit 4	Visit 5	Visit 6	Visit 7	Visit 8	Visit 9/ EOS			
Day	Day 1 (-12h) b	Day 1 (Dosing)	Day 2	Day 3	Day 4 (72h post) c	Day 8	Day 15	Day 22	Day 29 d	Day 43			
Visit Window	-	-	-	-	-	± 1 day	± 2 days	± 2 days	± 2 days	± 2 days			
Hematology, coagulation, chemistry, and urinalysis	X			X		X			X		X	AT follow-up (chemistry including ALT, AST, TB, and coagulation [optional if suspicion of drug-related ATs increased])	A sample should be collected before rescue treatment administration. If increase in: AT levels $> 3 \times$ ULN and/or TB $> 2 \times$ ULN, confirmation of abnormality will be required within 48-72h including ALT, AST, ALP, and TB, and afterwards weekly follow-up will be required at minimum; if early clinical symptoms of liver toxicity or DILI (e.g., anorexia, nausea, fatigue, right upper abdominal discomfort, vomiting) are present, the Investigator should start the same follow-up protocol indicated previously when any increase of AT and TB is present, unless there is an alternative explanation for the clinical symptoms and the liver enzymes increase.
Randomization		X											
Dosing		X	X h	X i									h Day 2 dosing applicable for Cohort B2 (2-day) in

Assessments & Procedures		Hospitalization					Out-patient Visits					Unscheduled Visit a	Notes
Visit Number	SCR	Visit 1	Visit 2	Visit 3	Visit 4	Visit 5	Visit 6	Visit 7	Visit 8	Visit 9/ EOS			
Day	Day 1 (-12h) b	Day 1 (Dosing)	Day 2	Day 3	Day 4 (72h post) c	Day 8	Day 15	Day 22	Day 29 d	Day 43			
Visit Window	-	-	-	-	-	± 1 day	± 2 days	± 2 days	± 2 days	± 2 days			
Temperature	X	X	X	X	X	X	X	X	X	X			The exact assessment timepoints during the hospitalization period are provided in Table 2 .
Adverse events		←===== Continuous =====→											
Concomitant medications	X	X	X	X	X	X	X	X	X	X			
Rescue treatment			As required										Rescue malaria treatment to be administered beginning Day 43 in Part A or as required.
Assessments only performed if the participant has been enrolled:													
Malaria and severe malaria signs and symptoms	X	X	X	X	X	X	X	X	X	X			
Blood films (microscopy)	X	X	X	X	X	X	X	X	X	X			Thick and thin blood films will be collected at Screening to confirm inclusion/exclusion criteria.

Assessments & Procedures		Hospitalization				Out-patient Visits					Unscheduled Visit a	Notes

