Visit Number	SCR	Visit 1	Visit 2	Visit 3	Visit 4	Visit 5	Visit 6	Visit 7	Visit 8	Visit 9/ EOS	a An unscheduled visit can be required due to AEs, increase in ATs, or CNS events.	b Dosing within 6 hours of disease diagnosis (at a maximum of 12 hours). c Hospitalization for 4 continuous days (72 hours post first dose). d Day 29, or day at premature discontinuation (Note: All Day 29 study evaluations will be done before antimalarial rescue treatment is provided).
Day	Day 1 (-12h) b	Day 1 (Dosing)	Day 2	Day 3	Day 4 (72h post) c	Day 8	Day 15	Day 22	Day 29 d	Day 43		
Visit Window	-	-	-	-	-	± 1 day	± 2 days	± 2 days	± 2 days	± 2 days		
												A thin blood smear should be reserved in the event of recrudescence, to confirm P. falciparum . The exact sampling timepoints during the hospitalization period are provided in Table 2.
		CCI	■	■	■	■	■	■	■	■		
CCCI			■	■	■		■	■	■	■		

Assessments & Procedures		Hospitalization					Out-patient Visits					Unscheduled Visit a	Notes
Visit Number	SCR	Visit 1	Visit 2	Visit 3	Visit 4	Visit 5	Visit 6	Visit 7	Visit 8	Visit 9/ EOS			
Day	Day 1 (-12h) b	Day 1 (Dosing)	Day 2	Day 3	Day 4 (72h post) c	Day 8	Day 15	Day 22	Day 29 d	Day 43			
Visit Window	-	-	-	-	-	± 1 day	± 2 days	± 2 days	± 2 days	± 2 days			
PK blood sampling for M5717		X	X	X	X	X	X	X	X	X		The exact sampling timepoints during the hospitalization period are provided in Table 2 . Not applicable for Pyramax (Cohort B3).	
PK blood sampling for pyronaridine		X	X	X	X	X	X	X	X	X		The exact sampling timepoints during the hospitalization period are provided in Table 2 . Not applicable for Pyramax (Cohort B3).	

CCI

ACPR= adequate clinical and parasitological response, AE=adverse event, ALP= alkaline phosphatase, ALT=alanine aminotransferase, AST=aspartate aminotransferase, AT=aminotransferase, CNS=central nervous system, DILI=drug-induced liver injury, ECG=electrocardiogram, EOS=end-of-study, PK=pharmacokinetic(s), RT-qPCR= reverse transcription quantitative real-time polymerase chain reaction, QTcF= corrected QT interval by Fridericia's formula, RT=reverse transcriptase, SCR=screening, TB=total bilirubin, ULN=upper limit of normal, WOCBP= woman of childbearing potential.

Table 2 Assessment and Sampling Timepoints During the Hospitalization Period: PK, Vital Signs, ECG, and Parasitemia

Assessment																		Notes

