	
Endpoint: Crude (polymerase chain reaction [PCR]-uncorrected) Adequate Clinical and Parasitological Response (ACPR) 28 and 42 days after treatment defined as absence of parasitemia (thick smear/microscopy), irrespective of axillary temperature, in participants who did not previously meet any of the criteria of ETF, LCF, or LPF
 
Target Population: See endpoint 3
 
Treatment: See endpoint 3
 
Intercurrent Event Strategy:
 
 • Intake of rescue medication at any timepoint: Composite variable strategy, i.e., endpoint is considered as treatment failure • Intake of prohibited medication that impacts treatment effect (e.g., drug with antimalarial activity) at any timepoint: Treatment policy strategy, i.e., treatment effect is estimated regardless of ICE • Experience of any event that affects absorption (i.e., vomiting within the study intervention absorptive period of $2 \times$ median t_{max}) or immune response (severe immunocompromised participants): Treatment policy strategy, i.e., treatment effect is estimated regardless of intercurrent event or Principal Stratum strategy • Premature study discontinuation at any timepoint due to lack of efficacy: Composite variable strategy • Death due to malaria at any timepoint: Composite variable strategy 
Population-level Summary: Crude ACPR rate at each timepoint, i.e., proportion of participants with crude ACPR at each timepoint
	6
	
Endpoint: PCR-adjusted ACPR 28 and 42 days after treatment defined as absence of parasitemia (thick smear/microscopy, after adjustment for parasitemia due to new infections as determined by genotyping using PCR techniques), irrespective of axillary temperature, in participants who did not previously meet any of the criteria of ETF, LCF, or LPF.
 
Target Population: see endpoint 3
 
Treatment: see endpoint 3
 
Intercurrent Event Strategy: see endpoint 6
	7

	
Population-level Summary: PCR-adjusted ACPR rate at each timepoint, i.e., proportion of participants with PCR-adjusted ACPR at each timepoint
	

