14.4 Late Parasitological Failure (LPF)

LPF is defined as presence of parasitemia on any day between 7 and 28 days after treatment (i.e., between Days 8 and 29) with temperature $< 37.5^{\circ}\text{C}$ in participants who did not previously meet any of the criteria of ETF or LCF.

The same ICE and strategies as defined for ACPR (see Section 14.1) will be applied for LPF, however, limited to events that occur between 7 and 28 days after treatment (i.e., between Days 8 and 29). Failure is considered presence of LPF.

The same analyses and population-level summaries as described for ETF will be applied for LPF.

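### The secondary 42-day ACPR is scored with a rescue cut-off and failure windows that are not tied to its Day 43 film

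*SAP*

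**What the plan says.** **Rescue.** SAP 14.1 applies its intercurrent-event rules as "handled as described in the following if the ICE takes place before 28 or 42 days post treatment". For rescue intake: "A composite variable strategy is applied, i.e., the primary endpoint is considered as failure (= presence of parasitemia and no ACPR"). Rescue is identified by filtering concomitant medications for named antimalarials, and by medical review. Nothing compares the intake with the time of the endpoint film, and nothing exempts treatment planned for the end of follow-up.

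SAP 5, endpoint 6, has a different rule: "Intake of rescue medication at any timepoint: Composite variable strategy, i.e., endpoint is considered as treatment failure". Endpoint 7 refers to endpoint 6, and endpoints 23 and 24 refer to 6 and 7.

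**Timing in Part A.** The note to the rescue row of protocol Table 1 reads "Rescue malaria treatment to be administered beginning Day 43 in Part A or as required". Note d to the same table protects one visit only: "All Day 29 study evaluations will be done before antimalarial rescue treatment is provided". No matching statement covers Day 43. SAP 9.4 gives a window of plus or minus 2 "days for Days 15, 22, 29 and 43", and under SAP 9.8 "time of treatment start is defined to be on Day 1".

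**Late recurrence.** The 42-day ACPR excludes only participants with an earlier ETF, LCF or LPF. SAP 14.4 states: "LPF is defined as presence of parasitemia on any day between 7 and 28 days after treatment (i.e., between Days 8 and 29"). The LCF window in SAP 14.3 also ends at Day 29. SAP 9.3 lists repeated and unscheduled measurements but, apart from technical repeats, does not analyse them.

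**The concern.** A 42-day cure rate should depend on what happened up to the film that decides it. Here the rescue rule runs to a fixed day, or has no limit, while the failure windows stop two weeks early.

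The first mismatch can make a participant with a negative film a failure because of a drug given afterwards. It can arise only in Part A, where Table 1 mentions treatment from Day 43. The second can make a recurrence a response, in either cohort.

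The 42-day rates matter because SAP 7 drops time to recrudescence, re-infection and re-emergence. Among the efficacy endpoints that can be read in the documents, the 42-day ACPR is the only one left that looks beyond Day 29. SAP 7 already corrected one mismatch of this kind: endpoints 7 and 24 had inherited a Day 4 limit on intercurrent events.

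**Working it through.** **Method check.** The only precision figure the plan states for ACPR is a lower 95% Wilson bound of about 85% for n = 50 and a rate of 95% (protocol 1.1, Number of Participants). The Wilson limits are [p + z²/2n ± z√(p(1−p)/n + z²/4n²)] / (1 + z²/n), with z = 1.96. Here (0.950 + 0.038 − 1.96 × √(0.00095 + 0.00038)) / 1.077 = 0.851. The figure is reproduced and is not in dispute.

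**Day arithmetic.** Days post treatment = study day − 1. The Day 43 visit may fall on Days 41 to 45.

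| Visit held on | Days post treatment | Before 42? | Rescue that day under SAP 14.1 | Under SAP 5 |
|---|---|---|---|---|
| Day 41 | 40 | yes | failure | failure |
| Day 42 | 41 | yes | failure | failure |
| Day 43 | 42 | no | not scored | failure |
| Day 44 | 43 | no | not scored | failure |
| Day 45 | 44 | no | not scored | failure |

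The two sections disagree on three of the five permitted days. On the other two they agree on failure, even when the film taken just before was negative.

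**Size in Part A.** Planned n = 12. Assume all 12 are otherwise responders and the drug follows the film. Each early case costs 1/12 = 8.3 points.

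| Visits on Day 41 or 42 with treatment given | 42-day ACPR | Wilson 95% CI |
|---|---|---|
| 0 | 12/12 = 100% | 75.8 to 100 |
| 1 | 11/12 = 91.7% | 64.6 to 98.5 |
| 2 | 10/12 = 83.3% | 55.2 to 95.3 |

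The documents do not say how often the visit falls early. If everyone is treated at the visit and each visit has an assumed 10% or 20% chance of being early, the chance of at least one early case is 1 − 0.9^12 = 72% or 1 − 0.8^12 = 93%.

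**Late recurrence.** No film is scheduled between the Day 29 and Day 43 visits. A recurrence in that interval is still a non-response if any of these applies:

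- the Day 43 film is positive (for the PCR-adjusted rate, unless it is a new infection);
- rescue is taken before the cut-off;
- the participant discontinues for lack of efficacy;
- the participant dies of malaria.

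What remains is an unscheduled positive film, negative again by the Day 43 film, with none of these events. One route is a prohibited drug with antimalarial activity that is not scored as rescue, because SAP 14.1 handles prohibited medication by treatment policy. Each such case adds 1/25 = 4 points in B0 at its planned size of 25.

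**The case against.** The strongest reply on rescue is that Table 1 names Day 43, not the Day 43 visit. Day 43 is 42 days post treatment, so on the calendar reading SAP 14.1 never scores that treatment. This stands as a possible reading, and the 14.1 problem depends on the other one. The SAP 5 wording would score the treatment on either reading.

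It is also unclear that cured Part A participants are treated at all. The Table 1 entry itself ends with an as-required clause. Protocol 6.6 ties rescue to failure of the intervention, and 6.8.1 lists the circumstances for rescue without a routine end-of-follow-up course. This stands as well: the documents do not settle it.

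Medical review under 14.1 could recognise an end-of-study course, but no rule tells the reviewer to set it aside. SAP 14.1 is the detailed derivation and may be meant to override the looser SAP 5 wording, which SAP 7 adopted to replace the Day 4 limit. The SAP does not say which section governs.

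A reader might infer that Part A would be reported near 58%, or at 0 of 12. The first needs visits spread evenly over the window, all 12 cured and all 12 treated at the visit. The second also needs all 12 to be treated, plus a literal reading of SAP 5 against 14.1. The documents support none of these combinations, and the protocol's own model (4.3) puts median 28-day ACPR for the Part A dose between 59.1% and 92.2%.

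A reader might also infer that any recurrence on Days 30 to 42 escapes the endpoint. It does not: most routes to failure remain open, and films up to Day 31 may belong to the Day 29 visit.

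**Conclusion.** The point holds as a mismatch of rules in a secondary endpoint.

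- **Rescue.** SAP 14.1 and SAP 5 give different rules, and neither asks whether rescue preceded the endpoint film. If Part A treatment is given at a visit on Day 41 or 42, each film-negative participant so treated lowers the 42-day rate by 8.3 points. This rests on the visit reading of Table 1, on the film being taken first, and on medical review not removing the case.
- **Late recurrence.** The gap is limited to unscheduled positives between the last two visits that clear without rescue, lack-of-efficacy discontinuation or malaria death. Its frequency cannot be derived from the documents.

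It would go too far to conclude that the main result or a comparison of cohorts is compromised. Under 14.1 the primary 28-day ACPR in B0 is untouched by the Part A rescue issue. SAP 7 plans no comparison of treatment groups, and SAP 9.1 reports Part A and B0 separately.

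**What to change.** 1. In SAP 14.1 and SAP 5 (endpoints 6, 7, 23 and 24), count rescue as failure for a timepoint only if it started before the film used for that timepoint, by actual date and time. If that film is missing, use the nominal day. Replace the unlimited wording in SAP 5 with this rule so that both sections agree.
2. For the 42-day ACPR only, count positive films after Day 29 up to the Day 43 film as failure. Include unscheduled films as a stated exception to SAP 9.3; extending the LCF and LPF windows alone would not bring them in. In the PCR-adjusted version, keep PCR-confirmed new infections as responders, as 14.1 requires.
3. Reconcile the Table 1 rescue note for Part A with protocol 6.6 and 6.8.1 on whether and when scheduled treatment is given.

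The cost is SAP wording, one date and time comparison, and use of unscheduled films already listed. No new data are needed.
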